### **2.2.2 Secondary Efficacy Endpoints**

Key secondary endpoints

- Proportion of subjects achieving corneal healing at Week 8 assessed by the CRC
- Proportion of subjects achieving corneal healing at Week 4 assessed by the CRC
- Time to corneal healing based on assessments by the CRC
- Time to  $\geq 20\%$  decrease in lesion size (maximum diameter) from baseline assessed by the CRC
- Proportion of subjects achieving corneal healing at each of Week 4, and Week 8 sustained for two weeks until Week 10 assessed by the investigator
- Proportion of subjects without persistent corneal staining during the study as assessed by the CRC
- Proportion of subjects with complete corneal healing and without persistent corneal staining during the study as assessed by the CRC

**Other secondary endpoints**

- Time to corneal healing based on assessments by the investigator
- Proportion of subjects achieving a  $\geq 15$ -letter gain in the study eye from baseline in pinhole distance VA at each of Weeks 4 and 8

**2.2.3 Exploratory Efficacy Endpoints**

- Proportion of subjects achieving corneal healing at each of Weeks 2, 6, and 8 assessed by the CRC
- Proportion of subjects with corneal healing defined as less than 0.5 mm fluorescein staining (the lower limit of reliable slit-lamp assessment) in the lesion area, assessed by the CRC at each of Weeks 4 and 8
- Time to  $\geq 20\%$  decrease in lesion area from baseline assessed by the CRC
- Change in lesion size (PED or ulcer maximum diameter) from baseline at each of Weeks 2, 4, 6, 8 and 10 assessed by the CRC
- Change in lesion area (PED or ulcer) from baseline at each of Weeks 2, 4, 6, 8 and 10 assessed by the CRC
- Change in pinhole distance VA in the study eye from baseline to each of Weeks 4 and 8 (and Week 10 in the subset of subjects completing Week 10)
- Proportion of subjects achieving a  $\geq 10$ -letter gain in the study eye from baseline in pinhole distance VA at each of Weeks 4 and 8
- Change in corneal sensitivity inside the lesion from baseline (measured by Cochet-Bonnet aesthesiometer) at Week 8 (data from the subset of subjects with this data)
- Change in Schirmer's test scoring at Week 8

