  - Subjects with corneal healing at Week 8 as assessed by the investigator will return at Week 10 for assessment of sustained healing. Schedule the subject for the next follow-up study visit (Week 10 Visit).
  - Subjects with incomplete corneal healing at Week 8 as assessed by the investigator will be unmasked. Sites will be provided instructions to unmask the subject using the IMB CD system.
    - Subjects randomized to vehicle will be eligible per investigator discretion to enter the uncontrolled treatment phase and receive 8-week treatment with CSB-001. See Section 6.2.
    - Subjects randomized to CSB-001 will exit the study and be treated per investigator discretion. See Section 6.3 for the study procedures required to be completed at the time of study exit.

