**6.1.10. Week 10 Visit (-2 to + 7 day window)**

Notes:

- It is critical that all subjects assessed as healed by the investigator at Week 8 return for the Week 10 Visit to ensure an adequate number of evaluable subjects for analysis. Site personnel will apply due diligence to contact the subject to return for the Week 10 Visit, even if outside the visit window. Subjects who return for the

Week 10 Visit more than 7 days than the actual visit date may not be eligible to enter the uncontrolled treatment phase.

- In cases where the CRC and investigator healing assessment differs at Week 8 and/or 10 (i.e., CRC assessed as healed and investigator assessed as not healed), and the subject did not enter the uncontrolled treatment phase, the Sponsor may request the subject to return to the clinic. At that visit, digital imaging of the cornea and logMAR pinhole distance VA will be completed at a minimum. The visit may be out of window and is acceptable.
  - Perform ophthalmic assessments in the study eye only
1. Record any changes in medical history and concomitant medications/therapies
  2. Record any adverse events since the last visit
  3. Perform logMAR pinhole distance VA
  4. Perform slit-lamp exam (without fluorescein staining)
  5. Perform digital imaging of the corneal fluorescein staining
    - Two sets of images will be captured at each timepoint where digital imaging is required. The first set of images will be collected  $30 \pm 15$  seconds after fluorescein instillation. The second set of images will be collected  $120 \pm 15$  seconds after fluorescein instillation.
  6. Perform investigator assessment of corneal healing and NEI scale assessment of corneal staining (additional fluorescein may be instilled per investigator discretion)
    - Subjects with corneal healing at Week 10 as assessed by the investigator will exit this study.
    - Subjects with incomplete corneal healing at Week 10 as assessed by the investigator will be unmasked. Sites will be provided instructions to unmask the subject using the IBM CD system.
      - Subjects randomized to vehicle will be eligible per investigator discretion to enter the uncontrolled treatment phase and receive 8-week treatment with CSB-001. See Section 6.2.
      - Subjects randomized to CSB-001 will exit the study and be treated per investigator discretion.

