**11.1.3. Exploratory Efficacy Endpoints**

- Proportion of subjects achieving corneal healing at each of Weeks 2, 6, and 8 assessed by the CRC
- Proportion of subjects with corneal healing defined as less than 0.5 mm fluorescein staining (the lower limit of reliable slit-lamp assessment) in the lesion area, assessed by the CRC at each of Weeks 4 and 8
- Time to  $\geq 20\%$  decrease in lesion area from baseline assessed by the CRC
- Change in lesion size (PED or ulcer maximum diameter) from baseline at each of Weeks 2, 4, 6, 8 and 10 assessed by the CRC
- Change in lesion area (PED or ulcer) from baseline at each of Weeks 2, 4, 6, 8 and 10 assessed by the CRC
- Change in pinhole distance VA in the study eye from baseline to each of Weeks 4 and 8 (and Week 10 in the subset of subjects completing Week 10)
- Proportion of subjects achieving a  $\geq 10$ -letter gain in the study eye from baseline in pinhole distance VA at each of Weeks 4 and 8
- Change in corneal sensitivity inside the lesion from baseline (measured by Cochet-Bonnet aesthesiometer) at Week 8 (data from the subset of subjects with this data)
- Change in Schirmer's test scoring at Week 8

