#### **Figure 1: Schematic of Study Design**

### Subjects randomized to CSB-001 in the controlled treatment phase

- Subjects with corneal healing at both Weeks 8 and 10 will exit the study at Week 10.
- Subjects with corneal healing at Week 8 that is not sustained for two weeks until Week 10 will exit the study at Week 10 and be managed per investigator discretion.
- Subjects whose cornea is not healed at Week 8 will exit the study at Week 8 and be managed per investigator discretion.

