### Subjects randomized to vehicle in the controlled treatment phase

- Subjects with corneal healing at both Weeks 8 and 10 will exit the study at Week 10.
- Subjects with corneal healing at Week 8 that is not sustained for two weeks until Week 10 are eligible to receive an 8-week course of CSB-001 treatment (uncontrolled treatment phase).
- Subjects whose cornea is not healed at Week 8 are eligible to receive an 8-week course of CSB-001 treatment (uncontrolled treatment phase).

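### The by-arm Week 10 change in lesion size and area is drawn almost entirely from eyes called healed at Week 8, so it is an outcome-selected summary and not a treatment comparison

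*SAP*

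**What the plan says.** SAP 2.2.3 lists "Change in lesion size (PED or ulcer maximum diameter) from baseline at each of Weeks 2, 4, 6, 8 and 10", as read by the CRC. Protocol 11.1.3 has the same item and its companion, "Change in lesion area (PED or ulcer) from baseline at each of Weeks 2, 4, 6, 8 and 10 assessed by the CRC". Neither carries a restriction at Week 10. In the same list, the visual acuity (VA) change endpoint does: its Week 10 value is confined by the words "and Week 10 in the subset of subjects completing Week 10".

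The SAP's general rules fix how the lesion endpoints will be shown. Tables are by treatment group (7.1), n counts non-missing values (7.3), nothing beyond the primary endpoint and partial dates is imputed (7.4), and exploratory endpoints are summarized descriptively (9.3).

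Attendance at Week 10 is set elsewhere. Protocol 6.1.9 states: "Subjects with corneal healing at Week 8 as assessed by the investigator will return at Week 10 for assessment of sustained healing". For the CSB-001 arm, SAP 3.0 states: "Subjects whose cornea is not healed at Week 8 will exit the study at Week 8 and be managed per investigator discretion". Vehicle subjects not healed at Week 8 are unmasked and may cross over to open-label CSB-001. Footnote 2 of the schedule of assessments in both documents agrees. Protocol 6.1.10 adds one exception: the sponsor may recall for imaging a subject whose two readings disagree ("CRC assessed as healed and investigator assessed as not healed") and who has not entered the uncontrolled phase.

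**The concern.** Weeks 2 to 8 describe every subject still on study. Week 10 describes a subset chosen by the outcome being measured: lesion status at Week 8 decides who is imaged two weeks later. If CSB-001 works, the selection removes more subjects from vehicle than from CSB-001, and those it removes are the ones with remaining lesions.

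Placed in one table, the series would show mean lesion reduction jumping between Weeks 8 and 10 and, in most scenarios, the arms drawing together. Selection alone can produce both features. A reader could take them to mean that vehicle catches up once dosing stops. The plan meets the problem for VA and leaves it open for the two endpoints where it bites hardest.

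**Working it through.** The documents give no figure for the Week 10 lesion endpoints. The figures used are the planning rates (60% and 30%, SAP 5.0) and 64 randomized per arm (SAP 4.0).

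**The plan's own calculation.** For 60% versus 30%, two-sided alpha 0.05 and 80% power, the two-proportion formula gives 42 per arm without continuity correction and 49 with it. The stated 48 is therefore close to a continuity-corrected figure, and 60%/30% are the operative rates. They are rates of *complete* healing (Week 8 sustained to Week 10), not of Week 8 healing, so two readings are carried forward.

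**Eyes imaged at Week 10, before dropout**

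- Reading A, rates taken as Week 8 healing: 64 × 0.60 = 38.4 and 64 × 0.30 = 19.2, about 38 versus 19.
- Reading B, sustained rates with 10% relapse in both arms: Week 8 healing is 0.60/0.90 = 66.7% and 0.30/0.90 = 33.3%. Then 64 × 0.667 = 42.7 and 64 × 0.333 = 21.3, about 43 versus 21.
- On the 48 per arm that SAP 4.0 expects to complete, Reading A becomes 48 × 0.60 = 28.8 and 48 × 0.30 = 14.4, about 29 versus 14.

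**Illustration.** These assumptions are not in the documents: baseline B = 4 mm in both arms, unhealed eyes improved by u = 1 mm, healed eyes at 0 mm at Week 8, relapsed eyes at s = 2 mm. Let p be Week 8 healing and r be relapse among healers.

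Week 8 mean change = −[pB + (1 − p)u]

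- Reading A: 0.6(−4) + 0.4(−1) = −2.8; 0.3(−4) + 0.7(−1) = −1.9; difference 0.9 mm.
- Reading B: 0.667(−4) + 0.333(−1) = −3.0; 0.333(−4) + 0.667(−1) = −2.0; difference 1.0 mm.

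Week 10 mean change among imaged eyes = −[B − rs]

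| Relapse, CSB-001 / vehicle | CSB-001 mean | Vehicle mean | Larger reduction |
|---|---|---|---|
| 10% / 10% | −3.8 | −3.8 | neither |
| 10% / 25% | −3.8 | −3.5 | CSB-001, by 0.3 mm |
| 25% / 10% | −3.5 | −3.8 | vehicle, by 0.3 mm |

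In general, the Week 8 difference is (pC − pV)(B − u), while the Week 10 difference is (rV − rC)s, plus any difference in mean baseline lesion size between the two sets of healers. The healing rates have dropped out of the second expression.

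**Range.** If unhealed eyes improve by 0 to 2 mm, the Week 8 difference in Reading A runs from 0.3 × 4 = 1.2 to 0.3 × 2 = 0.6 mm. This says nothing about Week 10, because unhealed eyes do not enter that mean. If 60%/30% are sustained rates and relapse is 10% versus 25%, Week 8 healing is 66.7% and 0.30/0.75 = 40%. The Week 8 difference is then 3.0 − [0.4(4) + 0.6(1)] = 3.0 − 2.2 = 0.8 mm, and the Week 10 difference is again 0.3 mm.

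A second set of assumptions (4 mm baseline, unhealed lesions at 60% of baseline, relapsed lesions at 40%) gives the same pattern. The difference over all randomized subjects is 0.67 to 0.77 mm. In the Week 10 subset it is 0 with equal relapse, and 0.17 to 0.24 mm with 10% to 14% relapse on CSB-001 and 25% on vehicle.

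**The case against.** The strongest reply is that little depends on this time point. The endpoints are exploratory, descriptive and untested. The table will print n, so the fall in numbers will be visible, and the exit rules are in the SAP itself. The primary endpoint already combines Weeks 8 and 10 and counts missing data as non-response. All of this stands, and it limits the consequence. It does not make the Week 10 mean interpretable: a visible n shows that subjects are absent, not that they were removed because of their lesions.

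SAP 3.0 also says in general terms that subjects return at Week 10. The same section then makes follow-up depend on the investigator's healing assessment, so that sentence does not supply images for unhealed eyes.

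Two stronger readings are tempting, and the documents support neither.

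- A reader might infer that only investigator-healed eyes can have Week 10 images. The recall provision in Protocol 6.1.10 is an exception. It is optional, however, and admits only eyes the CRC called healed, so the selection barely changes. Return also depends on the investigator's call while the endpoint is the CRC's measurement, so some returning eyes may have had a CRC lesion above 0 mm at Week 8.
- A reader might infer that the Week 10 summary erases any treatment effect. A difference of exactly 0 follows from giving both arms the same relapse and the same baseline among healers. With unequal relapse part of a difference remains, or its sign reverses.

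**Conclusion.** The point holds in this form: followed as written, the plan gives a Week 10 by-arm mean that conditions on Week 8 healing, a post-randomization outcome expected to differ between arms. It does not estimate a treatment effect and does not belong in one series with Weeks 2 to 8.

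The structural part rests on the documents alone. The counts (38 versus 19, or 43 versus 21, of 64 per arm before dropout) depend on how the planning rates are read. The size in millimeters rests on assumed lesion sizes and relapse rates. What carries over from the illustration is that the Week 10 difference reflects relapse and baseline among healers, not the healing rates. It may be much smaller than at Week 8, or of opposite sign, whatever the drug does. The change is worth making because it is cheap and the VA endpoint already sets the precedent, but no confirmatory conclusion depends on it.

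**What to change.** In SAP 2.2.3 and 9.3, end the by-arm series for change in lesion size and lesion area at Week 8. Make the same edit in Protocol 11.1.3, or record it as a change from the protocol, so that the endpoint lists do not disagree.

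Report Week 10 lesion data in a separate display: the number and proportion with a CRC lesion above 0 mm among Week 8 healers with imaging, with n per arm. Use the subset qualifier that the VA endpoint already carries. State that this is a post-randomization subset and not a treatment comparison, and say whose Week 8 call, investigator or CRC, defines healed.

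Do not rescue a Week 10 mean by carrying forward the Week 8 lesion of unhealed eyes. That is a single imputation which SAP 7.4 excludes for non-primary endpoints, and it assumes these eyes do not change for two weeks.

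The cost is wording in the endpoint lists and one table shell, with no new data. One exploratory time point is lost as a simple by-arm mean.

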**2.2.4 Safety Endpoints**

- Adverse events
- Slit-lamp examination
- Intraocular pressure (IOP)
- Dilated fundus ophthalmoscopy
- Visual acuity
- Ocular tolerability assessed by subjects

---

### 3.0 STUDY DESIGN

This is a multi-center, randomized, double-masked, vehicle-controlled, parallel-group safety and efficacy study.

[figure not shown]
Approximately 128 subjects with stage 2 or 3 NK will be randomized in a 1:1 ratio to the CSB-001 investigational treatment arm or vehicle control arm at approximately 50 investigative sites in the United States and Canada. All subjects will provide written informed consent prior to the conduct of any study procedures at the Day 0 Screening/Randomization Visit. Subjects must meet all study inclusion and exclusion criteria to qualify for enrollment in the study. Subjects will be required to discontinue all topical ophthalmic medications and contact lens use (both therapeutic and for refractive correction) in the study eye as noted in the exclusion criteria upon enrollment. The only exceptions are the allowance for use of preservative-free antibiotic eye drops if prescribed by the investigator and/or a non-preserved IOP-lowering topical ocular drop (with the exception of timolol) administered once-daily over the course of the study.

An initial safety phase is included whereby the first 12 randomized subjects will be evaluated by the masked Medical Monitor for dose limiting safety findings. Each subject will be assessed within three days of the Week 1 Visit. In the absence of an adverse event assessed as a dose limiting finding, enrollment of the remaining subjects will commence.

All subjects will dose with the randomized treatment QID for 8 weeks (referred to as the controlled treatment phase which includes the above initial safety phase). During the controlled treatment phase, subjects will return to the clinic weekly from Day 0 to Week 8, and again at Week 10. Subjects randomized to vehicle who are not healed at Week 8 or who are healed at Week 8 but do not remain healed at the Week 10 Visit are eligible to receive an 8-week QID course of CSB-001 (referred to as the uncontrolled treatment phase). See Schedule of Assessments, [Appendix 1](#).

Subjects will be followed as described below based on the randomized treatment arm and Week 8 and/or Week 10 investigator assessment of corneal healing. Subjects whose cornea is not healed (deemed non-responders) at the Week 8 or Week 10 Visit will be unmasked. See Schematic of Study Design, [Figure 1](#).

#### **Figure 1: Schematic of Study Design**

### Subjects randomized to CSB-001 in the controlled treatment phase

- Subjects with corneal healing at both Weeks 8 and 10 will exit the study at Week 10.
- Subjects with corneal healing at Week 8 that is not sustained for two weeks until Week 10 will exit the study at Week 10 and be managed per investigator discretion.
- Subjects whose cornea is not healed at Week 8 will exit the study at Week 8 and be managed per investigator discretion.

### Subjects randomized to vehicle in the controlled treatment phase

- Subjects with corneal healing at both Weeks 8 and 10 will exit the study at Week 10.
- Subjects with corneal healing at Week 8 that is not sustained for two weeks until Week 10 are eligible to receive an 8-week course of CSB-001 treatment (uncontrolled treatment phase).
- Subjects whose cornea is not healed at Week 8 are eligible to receive an 8-week course of CSB-001 treatment (uncontrolled treatment phase).

### Subjects randomized to vehicle who are eligible for, and enter, the uncontrolled treatment phase

- Subjects with cornea healing after the 8-week course of CSB-001 (Week 8 uncontrolled treatment phase visit) that is sustained for two weeks until Week 10 will exit the study at the Week 10 uncontrolled treatment phase visit.
- Subjects with corneal healing after the 8-week course of CSB -001 (Week 8 uncontrolled treatment phase visit) that is not sustained for two weeks until Week 10

---

will exit the study at the Week 10 uncontrolled treatment phase visit and be managed per investigator discretion.

- Subjects whose cornea is not healed after the 8-week course of CSB-001 (Week 8 uncontrolled treatment phase visit) will exit the study and be managed per investigator discretion.

#### **4.0 RANDOMIZATION AND BLINDING**

This is a multi-center, randomized, double-masked, vehicle-controlled, parallel-group safety and efficacy study. Approximately 128 subjects (64 per treatment arm) will be randomized in the study to complete approximately 96 subjects (48 per treatment arm).

#### **5.0 SAMPLE SIZE CONSIDERATIONS**

With the assumption that the proportion of subjects that will achieve complete corneal healing for the CSB-001 and vehicle are 60% and 30%, respectively, 48 subjects per arm (a total of 96 subjects) will have 80% power to detect the difference of 30% at a two-sided alpha 0.05 based on a Chi-squared test. With a predicted dropout rate of ~10% and the risk of inadequate numbers of corneal defect images for interpretation by the central reading center at key visits (Day 0, Week 8, and Week 10), approximately 128 subjects will be randomized at 1:1 ratio (CSB-001: vehicle).

#### **6.0 ANALYSIS POPULATIONS**

##### **6.1 Full Analysis Set (FAS)**

The full analysis set will include all subjects who are randomized regardless of exposure to test article. The full analysis set will exclude subjects who did not present with stage 2 or 3 NK at the screening visit per the CRC and any subjects who have no post-baseline images. Subjects will be classified according to the treatment at randomization. The full analysis set will be the primary population for evaluating all efficacy endpoints and subject baseline characteristics.

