### **13.2. Analysis Populations**

#### **13.2.1. Full Analysis Set**

The full analysis set will include all subjects who are randomized regardless of exposure to test article. The full analysis set will exclude subjects who did not present with stage 2 or 3 NK at the screening visit per the CRC. Subjects will be classified according to the treatment at randomization. The full analysis set will be the primary population for evaluating all efficacy endpoints and subject baseline characteristics.

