### **2.2.1 Primary Efficacy Endpoint and Estimand**

The primary efficacy endpoint is the proportion of subjects achieving complete corneal healing as defined above.

Primary Estimand for this study will be as follow:

- Treatment regimen: CSB-001 0.1% QID, and CSB-001 vehicle QID for 8 weeks
- Target population: Subjects with stage 2 or 3 NK in at least one eye as defined by the inclusion and exclusion criteria (per Protocol Section 4), grouped per randomization assignment
- Variable of interest: Responders defined as achieving complete corneal healing as defined above.
- Intercurrent events and corresponding strategy:
  - Subjects with missing Week 8 data for any reason will be imputed as non-responders
  - Subjects who demonstrate corneal healing at Week 8 and are missing Week 10 data will be imputed as non-responders
- Population-level summary measure: Difference in the proportions of responders.

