##### **6.2 Intention-to-Treat (ITT)**

The Intention-to-Treat will include all subjects who are randomized regardless of exposure to test article. The ITT population will include subjects who did not present with stage 2 or 3 NK at the screening visit per the CRC but exclude subjects who have no post-baseline images. Subjects will be classified according to the treatment at randomization. The ITT population will be used as a supplemental analysis for evaluating the primary endpoint.

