##### **6.3 Per-protocol Set (PPS)**

The per-protocol set will be a subset of FAS, excluding subjects who have any major protocol deviation which is likely to seriously affect the safety and efficacy outcomes of the study.

Evaluability will be assessed by subjects, visits and study procedures. The per-protocol set will be used to evaluate the primary efficacy endpoints as exploratory analyses.

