## 9.0 EFFICACY EVALUATION

### 9.1 Primary Efficacy Endpoint

#### 9.1.1 Primary Analyses

Analyses of the primary efficacy endpoint will follow the estimand framework stated in [Section 2.2.1](#). Full analysis set will be used for the efficacy analyses.

The primary efficacy endpoint is the proportion of subjects achieving complete corneal healing defined as absence of corneal staining in the area of the defect/ulcer (i.e., 0 mm lesion) at Week 8 and the absence of corneal staining in the area of the defect/ulcer (i.e., 0 mm lesion) two weeks later at Week 10 as assessed by a central reading center.

Chi-squared test will be used to compare each CSB-001 active treatment group (QID) to vehicle. The proportion and associated 95% confidence interval will be reported by each treatment arm. Difference in the proportions between treatment arms and associated 95% confidence interval will also be reported.

Missing data of the primary efficacy endpoint will be imputed as follow:

- Subjects with missing Week 8 data for any reason will be imputed as non-responders
- Subjects who demonstrate corneal healing at Week 8 and are missing Week 10 data will be imputed as non-responders

---

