### 9.1.3 Supplemental Analyses

Additionally, primary analysis based on ITT population will be repeated as a supplemental analysis.

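### The SAP removes subjects with no post-baseline image from both the FAS and the ITT set, so its own non-responder rule never reaches them and no efficacy analysis covers all randomized subjects

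*SAP*

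**What the plan says.** Protocol 13.2.1 builds the FAS from all randomized subjects with one exclusion, which is a baseline criterion: "The full analysis set will exclude subjects who did not present with stage 2 or 3 NK at the screening visit per the CRC".

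SAP 6.1 keeps that exclusion and adds a second, so that it drops subjects not judged stage 2 or 3 "per the CRC and any subjects who have no post-baseline images". SAP 6.2 defines an ITT set that readmits subjects whose stage the central reading center (CRC) did not confirm, "but exclude subjects who have no post-baseline images". Both SAP sections start from every randomized subject, dosed or not, and then take part of that back. SAP 6.3 adds no wider set: "The per-protocol set will be a subset of FAS".

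For the primary endpoint, SAP 9.1.1 states that "Full analysis set will be used for the efficacy analyses", and SAP 9.1.3 states that the "primary analysis based on ITT population will be repeated as a supplemental analysis". SAP 2.2.1 and 9.1.1 both give the missing-data rule: "Subjects with missing Week 8 data for any reason will be imputed as non-responders". SAP 1.0 says that its analyses take precedence over those in the protocol, so the narrower FAS governs. The SAP gives no reason for the change.

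**The concern.** Whether a subject has a post-baseline image is settled after randomization, and treatment can affect it. The first post-baseline imaging is at Week 1, and the early-exit procedures (Protocol 6.3 and Table 2) include no imaging. A subject who leaves the study before the Week 1 imaging, for instance because the first doses were not tolerated, would normally have no image and drop out of every efficacy analysis.

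Under the estimand each of these subjects is a failure. Removing failures shrinks the denominator and raises that arm's rate. If the arms lose different shares, the treatment difference is biased as well. The supplemental ITT analysis, which should show the effect of exclusions, cannot show this one because it makes the same exclusion.

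**Working it through.** **Reading the rules together.** No post-baseline image means no Week 8 CRC reading. No Week 8 reading means non-responder (SAP 2.2.1, 9.1.1). SAP 6.1 and 6.2 nevertheless remove the subject before that rule applies. The target population in SAP 2.2.1 has no image condition, so the analysis set does not match the estimand. The sensitivity analyses in SAP 9.1.2 name no wider set, and the tipping-point analyses start from the reduced denominators.

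**The plan's own figure.** Inputs from SAP 4.0 and 5.0: 60% versus 30%, two-sided alpha 0.05, 80% power, 48 per arm, 64 per arm randomized.
- Uncorrected chi-squared: n = [1.960·√(2·0.45·0.55) + 0.842·√(0.60·0.40 + 0.30·0.70)]² / 0.30² = 42 per arm.
- With continuity correction: 49 per arm. Exact power of the corrected test at 48 per arm is 80.0%, so the stated 48 reproduces.
- 1 − 96/128 = 25%. The randomized number therefore allows for 25% total loss.

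**Effect on the estimate.** Let f be the share of an arm with no post-baseline image. *Assumption:* imaged subjects respond at 60% and 30%. The estimand rate is then the imaged rate × (1 − f). The SAP difference is 60 − 30 = 30.0 points whatever f is.

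| f, CSB-001 | f, vehicle | Estimand rates | Estimand difference | SAP minus estimand |
|---|---|---|---|---|
| 5% | 5% | 57.0% vs 28.5% | 28.5 | +1.5 |
| 10% | 5% | 54.0% vs 28.5% | 25.5 | +4.5 |
| 5% | 10% | 57.0% vs 27.0% | 30.0 | 0.0 |
| 0% | 5% | 60.0% vs 28.5% | 31.5 | −1.5 |

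**Effect on the p-value.** This is a constructed borderline table: 64 per arm, vehicle 19/64, 29 responders on CSB-001, no-image subjects on CSB-001 only, uncorrected chi-squared test.
- All randomized: 29/64 = 45.3%, p = 0.068.
- Two excluded: 29/62 = 46.8%, p = 0.048.
- Four excluded: 29/60 = 48.3%, p = 0.033.
- Six excluded: 29/58 = 50.0%, p = 0.022.

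**Effect on the error rate.** Suppose the all-randomized response rate is 30% in both arms and m failures are dropped from CSB-001 only. The analyzed CSB-001 rate becomes 0.30·64/(64 − m). The exact two-sided rejection rate is 5.1% for m = 0, 5.4% for m = 3, 6.2% for m = 6 and 10.5% for m = 10.

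**The case against.** The strongest reply concerns size.
- **Reach.** The exclusion affects only subjects with no post-baseline image at all. One image at Week 1, 2, 3, 4 or 6 keeps a subject in the FAS, and a missing Week 8 then counts as failure, as intended.
- **Mechanism.** Protocol 8.1 asks subjects who stop treatment to come in for follow-up and to continue scheduled visits. Stopping drug is therefore not the same as having no image.
- **Rates.** Predicted dropout is about 10% for the whole study. The 10%/5% case averages 7.5% and places most of that before the first image. One such subject among 64 moves a 60.0% rate only to 59.1%, and two move it to 58.1%.
- **Direction.** Nothing in the documents shows which arm would lose more subjects, and the last two rows of the table show no overstatement or an understatement.
- **Visibility.** Disposition (SAP 8.1) reports the randomized, FAS and ITT counts, and the safety set keeps every dosed subject.
- **Starting point.** The protocol's FAS was not all randomized subjects either.

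All of this stands as a limit on magnitude, and the effect may be small. It does not remove the conflict between the set definitions and the estimand, and it supplies no planned efficacy analysis that includes these subjects. An unknown direction is a reason not to let the analysis depend on it.

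**Conclusion.** The concern holds. For subjects with no post-baseline image, the primary analysis departs from the SAP's own estimand and from the protocol's FAS, and neither the ITT nor the per-protocol analysis brings them back. The statement that no analysis covers all randomized subjects refers to efficacy only.

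Under the assumed shares of 0% to 10% per arm tabulated above, the SAP's difference ranges from 1.5 points too small to 4.5 points too large. These figures rest on two assumptions: the no-image shares, which the documents do not give, and the application of 60% and 30% to imaged subjects. Two excluded subjects in one arm are enough to carry a borderline result across 0.05. Because the exclusion acts on the primary p-value, it should be settled before the controlled-phase data are unblinded.

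**What to change.** Delete the image condition from SAP 6.1 and 6.2. The FAS then matches Protocol 13.2.1: all randomized subjects except those whose stage 2 or 3 disease at screening was not confirmed by the CRC. The ITT set becomes all randomized subjects. Subjects with no post-baseline image enter both as non-responders under SAP 9.1.1.

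The cost is two clauses and slightly lower reported response rates. With 64 per arm and equal no-image shares, power by the uncorrected normal approximation, after the fix and with the exclusion kept, is:

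| No-image share per arm | Difference after fix | Power after fix | Power with exclusion |
|---|---|---|---|
| 5% | 28.5 points | 91.3% | 92.4% |
| 10% | 27.0 points | 88.4% | 91.0% |
| 15% | 25.5 points | 85.2% | 89.3% |
| 25% | 22.5 points | 77.4% | 85.1% |

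These figures consider this source of loss alone. Power stays above 80% at shares up to 15%. It falls below 80% in the last row, where the entire 25% loss allowance consists of no-image subjects. On this point the sample size need not change.
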